2.3.3.2 ANALYSIS OF PROPORTIONS FOR KEY SECONDARY ENDPOINTS

For the between-group comparison of proportions (endpoint 11 in the hierarchy noted above), the key secondary hypothesis is that the proportion of subjects who achieve dryness using Vital Compact is not less than the proportion who achieve dryness using itouch Sure Pelvic Floor Exerciser:

$$H_0: p_{Neurotech\ Vital\ Compact} - p_{control} \leq 0\%$$

$$H_1: p_{Neurotech\ Vital\ Compact} - p_{control} > 0\%$$

where $p_{Neurotech\ Vital\ Compact}$ is the proportion of subjects who achieve dryness on Vital Compact and $p_{control}$ is the proportion of subjects who achieve dryness on iTouch Sure Pelvic Floor Exerciser.

To test this hypothesis, a Chi-Square test will be conducted. The difference between device groups will be summarized and a 95% CI of the difference will be calculated using the normal approximation to the binomial distribution. The counts and proportions of subjects achieving dryness for each device group will be summarized along with the exact 95% confidence interval.

2.3.3.3 ANALYSIS OF WITHIN-GROUP MEAN CHANGES FOR KEY SECONDARY ENDPOINTS

For the within-group comparisons of mean change (endpoints 2, 4, 6, 8, and 10 in the hierarchy noted above), the key secondary hypothesis is that the mean change from baseline to Week 12 within the Vital Compact group is not equal to 0:

$$H_0: \mu_{Vital\ Compact} = 0$$

$$H_1: \mu_{Vital\ Compact} \neq 0$$

where $\mu_{Vital\ Compact}$ is the mean change from baseline for the Vital Compact group.

To test this hypothesis, a one-sample t-test will be conducted for each endpoint. The Week 12 summaries for each device group will include the number of observations, mean, median, standard deviation, minimum, maximum, and 95% confidence interval. In the event that data are highly non-normal, non-parametric methods (e.g. signed-rank test) may be employed. Normality will be tested using Shapiro-Wilk Test.

2.3.4 OTHER SECONDARY ENDPOINTS

Additional secondary endpoints will be summarized with descriptive statistics for the ITT population. There are no formal statistical tests associated with these endpoints and missing data will not be imputed.

The secondary endpoints that will be evaluated at 4 weeks and 26 weeks are as follows:

- Proportion of subjects considered to have achieved significant improvement, defined as a greater than 50% reduction in urine leakage from baseline on the provocative pad weight test;
- Urine leakage on the provocative pad weight test;
- Urine leakage experienced by the subject at home in the 24-hour pad weight test;
- Incontinence episodes/day recorded using a 7-day voiding diary;
- Proportion of subjects achieving dryness (<1g urine leakage on the provocative pad weight test);

- Improvement in quality of life assessed using the Incontinence Quality of Life Questionnaire (I-QOL);
- Number of pads/day recorded using a 7-day voiding diary;
- Proportion of subjects achieving dryness, defined as a urine leakage of less than 1.3g on the 24-hour pad weight test;
- Proportion of subjects considered to have achieved a greater than 50% reduction in urine leakage, from baseline on the 24-hour pad weight test.

Additional Week 12 endpoints include:

- Proportion of subjects considered to have achieved a greater than 50% reduction in urine leakage, from baseline on the 24-hour pad weight test;
- Proportion of subjects achieving dryness, defined as a urine leakage of less than 1.3g on the 24-hour pad weight test;
- Proportion of subjects achieving dryness in each group (<1g urine leakage on the provocative pad weight test);
- Mean change, with respect to baseline, in sexual function as measured by the Pelvic Organ Prolapse/Urinary Incontinence Sexual Questionnaire (PISQ-IR);
- Estimates of subject response to the Subject Global Impression of Improvement (PGI-I).

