6.2 Inclusion Criteria

1. Subjects who are female and at least 18 years of age, and not more than 65 years of age.
2. Subjects who have signed the informed consent form prior to any study related activity.
3. Subjects who have previously tried and failed to improve their condition using Kegel exercises.
4. Subjects who have been clinically diagnosed with stress urinary incontinence and demonstrate a greater than or equal to 3g urine leakage and a less than or equal to 90g urine leakage ($\geq 3g$ and $\leq 90g$) following a bladder-filling protocol and then a standardised stress test (provocative pad weight test) at the baseline assessment.
5. Subjects who score 9 or less (≤ 9) out of 18 for the Urge Incontinence Questions and are confirmed as having predominant stress urinary incontinence on the Medical, Epidemiologic and Social Aspects of Aging Urinary Incontinence (MESA) Questionnaire completed at the screening assessment.
6. Subjects with a Body Mass Index of $\leq 35 \text{ kg/m}^2$.
7. Subjects of child-bearing potential who are using a highly effective contraceptive method (established use of oral, injected, implanted hormonal method of contraception or barrier method of contraception with spermicide).
8. Subjects who are willing not to seek any other treatment for stress incontinence during the study period.
9. Subjects who are able to give voluntary, written informed consent to participate in this study and from whom consent has been obtained.
10. Subjects who are able to understand this study and are willing to complete all the study assessments.

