test). The data from this test will not be used for analysis purposes, it is only to allow patients to practice the stress test. Further details of the stress test protocol and instructions for the Investigator and subject are provided in Appendix III.

- Record any cough or cold symptoms.
- Record any adverse events.

Prior to leaving the clinic, subjects will also be provided with the following:

- A 7-day voiding diary to complete seven days prior to the Visit 2 (baseline) appointment.
- Pre-weighed incontinence pads in a sealed bag to complete the 24-hour pad collection for three days prior to the Visit 2 (baseline) appointment.

The subject will then be asked to return the 7-day voiding diary and incontinence pads in the same sealed bag to the clinic at Visit 2. Any subjects menstruating during the three days prior to Visit 2 will also be asked to record this on the voiding diary. Any subjects who have sexual intercourse during this three day period will be asked to expel any fluid post-intercourse and also record this on the voiding diary.

8.10 Baseline Assessments – Visit 2

On the subject's return to the clinic to return the 7-day voiding diary and incontinence pads, the following information/procedures will be recorded:

- Complete the Incontinence Quality of Life Questionnaire (I-QOL) (patient quality of life questionnaire).
- Complete the Pelvic Organ Prolapse/Urinary Incontinence Sexual Questionnaire (PISQ-IR).
- Complete a standardized stress test to evaluate amount of urine lost following a standardized bladder-filling protocol verified by ultrasound bladder scanning (provocative pad weight test). This assessment will be used to determine the subject's eligibility to participate. Further details of the stress test protocol and instructions for the Investigator and subject are provided in Appendix III.
- Number of incontinence episodes/day from 7-day voiding diary.
- Number of pads used/day from 7-day voiding diary.
- Mean weight of urine leaked during three consecutive 24-hour periods at home (difference in post- and pre-weight incontinence pads) (24-hour pad weight test). Severity score will be assessed as dry (less than 2g), mild (greater or equal to 2g and less than 10g), moderate (greater or equal to 10g and less than 50g) and severe (greater than 50g) (O'Sullivan, 2004).
- Record any medication use or changes in medication since the last visit.
- Record any cough or cold symptoms since the last visit.

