3.4 SEVERITY OF STRESS URINARY INCONTINENCE

The severity of stress urinary incontinence will be defined as dry (< 1.3g), mild (1.3g to < 20g), moderate (20g to < 75g) and severe ($\geq 75g$), based on the 24-hour pad weight test (O'Sullivan, 2004).

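### Women already below 1.3 g on the 24-hour pad test at baseline can be randomised, and SAP 2.3.4 would count them as achieving 24-hour dryness if they simply stay there

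*SAP*

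**What the plan says.** **Entry.** Inclusion criterion 4 (Protocol 6.2) requires that women "demonstrate a greater than or equal to 3g urine leakage and a less than or equal to 90g urine leakage" on the provocative test at baseline. Protocol 8.10 says of that test: "This assessment will be used to determine the subject's eligibility to participate". The schedule in Appendix I attaches eligibility to the same test and to no other leakage measure.

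**The 24-hour test at baseline.** Protocol 8.10 also records "Mean weight of urine leaked during three consecutive 24-hour periods at home" at Visit 2, but no inclusion or exclusion criterion in Protocol 6.2 or 6.3 uses it.

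**Severity classes.** Protocol 8.10 grades the 24-hour result: "Severity score will be assessed as dry (less than 2g", and so on upwards. SAP section 4 says those ranges were wrong and replaces them. SAP 3.4 now reads "The severity of stress urinary incontinence will be defined as dry (< 1.3g", which is the cut-off used by the dryness endpoint.

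**The endpoints.** SAP 2.3.4 lists 24-hour dryness, "Proportion of subjects achieving dryness, defined as a urine leakage of less than 1.3g on the 24-hour pad weight test", and 24-hour response, "Proportion of subjects considered to have achieved a greater than 50% reduction in urine leakage, from baseline on the 24-hour pad weight test". Both are reported at Weeks 4, 12 and 26 for the ITT population, without imputation and without formal tests. ITT means everyone randomised; under SAP 2.1 the modified set drops only women who never used the device.

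**The concern.** To achieve dryness suggests moving from wet to dry. As written, the endpoint records status at the visit, whatever the starting point. A woman at 0.5 g before and after treatment enters the numerator. On the 50% endpoint, a woman going from 0.6 g to 0.2 g is a responder (a 67% reduction on a change of 0.4 g), and a woman at 0 g has no percentage change at all; the SAP gives no rule for her.

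The provocative dryness endpoint (below 1 g) does not share the problem. Every eligible woman starts at 3 g or more on that test, so being dry at Week 12 is a conversion.

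At stake is how two descriptive rates are read. Each arm's 24-hour dryness rate could include women with nothing to gain. That would raise both rates and usually narrow the gap between them.

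**Working it through.** The documents state no figure for 24-hour dryness or for the share of women dry at home at baseline, so there is no plan figure to reproduce.

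**Formula.** Let b be the share with baseline 24-hour leakage below 1.3 g, s the share of those still below 1.3 g at the visit, and c the conversion rate among women at 1.3 g or more at baseline. Then

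- reported rate = b·s + (1 − b)·c
- excess over true conversion = b·(s − c), which is positive whenever s > c.

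**A rough value for b from the documents.** Protocol 2.1 reports pilot 24-hour leakage before treatment of 21.8 g (SD 19.41); sixteen women completed baseline measurements. Two skewed distributions matched to that mean and SD:

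- Lognormal: σ² = ln(1 + (19.41/21.8)²) = 0.584, σ = 0.764, μ = ln 21.8 − 0.584/2 = 2.790. P(below 1.3 g) = Φ((ln 1.3 − 2.790)/0.764) = Φ(−3.31) ≈ 0.05%.
- Gamma: shape (21.8/19.41)² = 1.26, scale 19.41²/21.8 = 17.3. P(below 1.3 g) ≈ 3.2%.

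Of 180 women that is between 0.08 and 5.8, so roughly 0 to 6.

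**Reported rate, with s = 0.9 assumed throughout.**

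| b | source of b | c = 20% | c = 40% |
|---|---|---|---|
| 0.05% | pilot, lognormal | 20.0% | 40.0% |
| 3.2% | pilot, gamma | 22.2% | 41.6% |
| 10% | assumed | 27% | 45% |
| 20% | assumed | 34% | 50% |
| 30% | assumed | 41% | 55% |

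For example, at b = 10% and c = 20%: 0.10 × 0.9 + 0.90 × 0.20 = 0.27. At b = 10%, 9 of 90 women per arm start below the cut-off.

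**Between arms.** With equal b and s, the b·s term cancels and the difference becomes (1 − b)(c₁ − c₂). Conversion of 40% against 20% at b = 10% is reported as 45% against 27%, so 20 points become 18. If b differs by chance, the difference can move either way. With b of 15% and 5% and the same c in both arms, the spurious difference is 0.10 × (0.9 − c): 7 points at c = 20%, 5 points at c = 40%.

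**Does anything else in the plan correct this?** SAP 2.2 summarises baseline incontinence data, which gives context but leaves the rates as they are. SAP 2.7 uses baseline severity as a subgroup factor for the primary endpoint and for change in provocative leakage, not for the 24-hour endpoints.

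**The case against.** Four points on the other side carry weight.

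- **Expectation.** A reader might infer from the dry class in Protocol 8.10 and SAP 3.4 that the authors expect such women. The documents do not support that. The class comes with a scale the SAP attributes to a cited reference, and listing every class is not a forecast that each will be filled; the BMI subgroups in SAP 2.7 likewise include underweight. Entrants also need a clinical diagnosis, failed Kegel exercises and stress predominance on MESA. The text shows only that women dry at home are not excluded.
- **Size.** A reader might take 10 to 30% as the likely share. Nothing in the documents points there, and the only 24-hour data they contain suggest 3% or less. The pilot is weak evidence, being small and having mean clinic leakage of 41.6 g, whereas this trial admits women from 3 g. Low values of b must stay in the range; higher ones cannot be ruled out.
- **Consequence.** Protocol 10.3.8 says these endpoints carry no formal tests and no labelling claims. The hierarchy's 24-hour endpoints (3 and 4) are mean changes, to which a woman at 0.5 g before and after contributes zero.
- **Estimand.** Protocol 5.3 defines 24-hour dryness as a pad weight at the visit. The proportion dry among all randomised women is a legitimate ITT summary, and randomisation balances baseline dryness in expectation.

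These limit the point to a low-severity one. They do not remove it: the SAP wording presents a status as an achievement, the percentage endpoint has no value at 0 g, and no planned table separates women who converted from women who were already dry.

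**Conclusion.** The gap in definition is certain from the text. Its size is not. On the pilot-based range for b (about 0 to 3%) the 24-hour dryness rate is inflated by about 2 points or less. Only at an assumed b of 10 to 30% does it become material: 7 to 21 points at a true 20%, 5 to 15 points at a true 40%. These figures take s = 0.9, which is also an assumption.

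A reader might infer that the trial's efficacy conclusion is inflated. It is not. The primary endpoint, the testing hierarchy and provocative-test dryness (key secondary endpoint 11) are unaffected, and so is the type I error. Nor does the inflation by itself favour either device: equal shares of baseline-dry women dilute a difference, and only a chance imbalance could distort it, in either direction. This is a cheap improvement to two descriptive endpoints.

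**What to change.** In SAP 2.3.4, report 24-hour dryness and 24-hour reduction of more than 50% at each visit among women whose baseline 24-hour leakage is 1.3 g or more (mild, moderate or severe in SAP 3.4), alongside the all-ITT figure. State per arm how many women were below 1.3 g at baseline and how many have no baseline value; SAP 3.2 allows a value to be indeterminable when used pads are not returned. For the all-ITT version of the 50% endpoint, add a line on how a baseline of 0 g is handled. Eligibility stays as it is.

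The cost is a few lines of SAP text and a filter on a variable already derived. Protocol 8.8 requires baseline assessments to be finished before randomisation, so restricting on the baseline value keeps the arms comparable. Setting the denominator before unblinding also avoids choosing it after seeing the data.

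The downside is a slightly smaller denominator. The restriction does not remove weighing error just above the cut-off: 1.4 g to 0.6 g would still count as a response. If few or no women are below 1.3 g at baseline, the two displays will agree closely and the question is settled.

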2.4 SAFETY ENDPOINTS

2.4.1 DEVICE USE

Device use will be summarized for each device using the daily device diary for the safety population. The following parameters will be included:

- Average number of sessions per week
- Average duration per session
- Average intensity per session
- Percent of actual use
- Percent of target use

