7.7 Treatment Compliance

Compliance will be assessed by reviewing the medical chart for information regarding the date and time of study visits. At each visit, information will be obtained from the devices (depending on the device) including treatment time, highest intensity reached and average intensity. In addition, subjects will be asked to complete a daily record of device use which will capture the duration of treatment and the maximum intensity reached during that session.

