8.11.5 Assessments

At each visit the following information/procedures will be recorded by the designated blinded site personnel:

- Urine pregnancy test to confirm subject is not pregnant (women of child-bearing potential only) (Week 4 only).
- Complete the Incontinence Quality of Life Questionnaire (I-QOL) (patient quality of life questionnaire).
- Complete the Pelvic Organ Prolapse/Urinary Incontinence Sexual Questionnaire (PISQ-IR) (Week 12 only).
- Complete the Patient Global Impression of Improvement (PGI-I) (Week 12 only).
- Complete a standardized stress test to evaluate amount of urine lost following a

standardized bladder-filling protocol verified by ultrasound bladder scanning (provocative pad weight test). Further details of the stress test protocol and instructions for the Investigator and subject are provided in Appendix III.

- Number of incontinence episodes/day from 7-day voiding diary.
- Number of pads used/day from 7-day voiding diary.
- Mean weight of urine lost during a three day 24-hour period at home (difference in post- and pre-weight incontinence pads) (24-hour pad weight test).
- Record any medication use or changes in medication since the last visit.
- Record any cough or cold symptoms since the last visit.
- Record any adverse events since the last visit.

At this visit the following information/procedures will be recorded by the designated unblinded site personnel only:

- Hydrogel electrodes will be checked and replaced with new electrodes if required (Neurotech Vital Compact device only).
- Data from the device will be recorded to determine stimulation parameters and duration of treatments that were completed according to the planned treatment programme. If usage information has been inadvertently erased, the device record provided by the patient may be used to provide compliance data.

At Visit 3 and Visit 4 subjects will be provided with a 7-day consecutive voiding diary and pre-weighed incontinence pads in a sealed bag to complete prior to the next visit. Subjects will be reminded to return the 7-day voiding diary and incontinence pads in the same sealed bag to the clinic at the next visit. Any subjects menstruating during the three days prior to the next visit will also be asked to record this on the voiding diary. Any subjects who have sexual intercourse during this time will be asked to expel any fluid post-intercourse and will be asked to record this on the voiding diary.

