3.7.1 AVERAGE NUMBER OF SESSIONS PER WEEK

The average number of sessions per week is calculated as

$$\text{Average Number of Sessions per Week} = \frac{\text{number of sessions used}}{\text{duration of treatment}} * 7$$

where the number of sessions used is obtained from the daily record and the duration of treatment is the relative day of the Week 12 visit minus 1.

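### The SAP takes device use and average intensity from the patient diary, whereas the protocol reads the devices where it can and says the diary records each session's maximum

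*SAP*

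**What the plan says.** **SAP.** Section 2.4.1: "Device use will be summarized for each device using the daily device diary for the safety population". One of the listed parameters is "Average intensity per session". Section 3.7.1 calculates sessions per week, "where the number of sessions used is obtained from the daily record". Sections 3.7.2 and 3.7.3 use the same source for percent of actual use and percent of target use. Section 2.7 forms subgroups by average stimulation intensity over the 12 weeks, with cut-points of 30, 60 and 90 for Vital Compact and 25, 50 and 75 for itouch Sure. It names no data source. Section 2.1 makes compliance a per-protocol criterion, again with no source or threshold.

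**Protocol.** Section 7.7 says that at each visit "information will be obtained from the devices (depending on the device) including treatment time, highest intensity reached and average intensity". It adds that subjects keep "a daily record of device use which will capture the duration of treatment and the maximum intensity reached during that session". The synopsis, section 8.11.5 and Appendix I have device data taken at Weeks 4 and 12; the synopsis and 8.11.5 assign this to unblinded staff. Section 8.11.5 continues: "If usage information has been inadvertently erased, the device record provided by the patient may be used to provide compliance data". Section 6.5 is looser and allows either internal memory or the diary for checking daily use. The form in Appendix VIII asks for stimulation intensity without saying maximum or average.

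SAP section 4, which lists departures from the protocol, does not mention a change of source.

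**The concern.** Device compliance in each arm, and leakage reduction in relation to the mean intensity delivered, are both listed for evaluation (protocol 5.3 and 10.3.8). If the SAP is followed as written, the device-use tables will rest on self-report from women who know which device they have, while a device record already collected at two visits goes unused. The table labelled average intensity would hold a different quantity from the one the protocol names. An undeclared change of source also leaves a reader of the final report unable to tell which record was used.

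**Working it through.** **Sources side by side**

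| Item | Device, per protocol | Patient record, per protocol | SAP source |
|---|---|---|---|
| Sessions | Counted by Vital Compact (Appendix XI) | Daily entries | Daily record (3.7.1 to 3.7.3) |
| Duration | Treatment time (7.7) | Yes (7.7, Appendix VIII) | Diary (2.4.1) |
| Maximum intensity | Yes (7.7) | Yes (7.7) | Not requested |
| Average intensity | Yes, depending on the device (7.7) | Not asked for | Diary (2.4.1); unstated in 2.7 |

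The last row is the mismatch: the SAP asks the diary for an item that 7.7 assigns to the device.

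**Could storage limits explain the choice for Vital Compact?** The SAP's prescribed totals reproduce: 12 × 7 = 84 for itouch Sure and 5 × 12 = 60 for Vital Compact. Appendix XI says the controller stores maximum intensity, average intensity and duration for 90 sessions, and 90 exceeds 60. Split sessions are allowed (two of 15 minutes or three of 10), which gives 60 × 2 = 120 or 60 × 3 = 180 records. If per-session data are read at Week 4:
- Weeks 1 to 4 hold 4 × 5 = 20 treatment days, so at most 20 × 3 = 60 records. All fit.
- Weeks 5 to 12 hold 8 × 5 = 40 treatment days: 40 × 2 = 80 records fit, and 40 × 3 = 120 records overrun by 30.

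Per-session data would therefore be lost only for women who split nearly every session into three. Even then the running total of treatment time goes to almost 200 hours, against 60 × 30 minutes = 30 hours prescribed. These counts ignore visit windows and the clinic training session.

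**How far can a maximum stand above an average?** The documents give no figure, so this is an illustration. Assume the setting rises linearly to its maximum over the first r minutes of a T-minute session and is then held. Then average / maximum = 1 − r/(2T).

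| Device | T (min) | r = 2 | r = 5 | r = 10 |
|---|---|---|---|---|
| Vital Compact | 30 | 0.967 | 0.917 | 0.833 |
| itouch Sure | 20 | 0.950 | 0.875 | 0.750 |

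If diary maxima were placed in the SAP 2.7 bands, a woman would be filed as high with a true average at or below the medium limit when her maximum lies:
- for Vital Compact, above 60 and up to 60/0.967 = 62.1 (r = 2) or 60/0.833 = 72.0 (r = 10);
- for itouch Sure, above 50 and up to 50/0.950 = 52.6 (r = 2) or 50/0.750 = 66.7 (r = 10).

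The error runs in one direction only. For the same rise time it is larger in the itouch arm, because that session is shorter.

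**The case against.** The case for the SAP has substance.

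- **The protocol is not uniform.** Section 6.5 permits the diary as an alternative, 7.7 qualifies device data by device, and 7.7 collects the diary from everyone. It would be tempting to say that the protocol treats the diary purely as a fallback and the SAP reverses it. The documents do not go that far: only 8.11.5 ranks the two sources, and only for erased data. What stands is that no protocol section makes the diary the sole source for both devices.
- **The form does not say maximum.** That description rests on 7.7. But the form does not ask for an average either.
- **The SAP phrase may mean an average across sessions of the recorded value.** That is a fair reading, since it sits beside average duration. It still yields a mean of maxima if 7.7 is followed.
- **The diary is the one record collected alike in both arms.** Appendix XII describes memory of the last settings for itouch Sure but no log of average intensity, although protocol 2.4 and 6.5 refer to a compliance monitor and internal memory. This is a good reason to keep a diary summary. The SAP does not give it.
- **Average and maximum may be close.** Appendix XI says the Vital Compact timer starts counting down once the intensity is set.

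A reader might also infer that the SAP 2.7 bands will be filled with diary maxima, or that self-report decides per-protocol membership. Neither section names a source, so both remain possibilities. Nor is self-report uncheckable here: the device data are the check.

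**Conclusion.** The point holds as a conflict over data source and variable definition. The SAP bases sessions, duration and intensity on the diary in both arms, the protocol takes these items from the device where available, and the change is not declared. A diary-based average intensity would be a mean of self-reported maxima, not the mean intensity delivered.

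The certain effect is confined to the device-use and compliance summaries, which carry no formal test or labelling claim. The effects on the intensity subgroups, including their interaction p-value, and on the per-protocol population are conditional on those analyses using the diary. The primary intent-to-treat comparison does not use device-use data and is unaffected.

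The conclusion rests on 7.7 for what the diary holds and on 8.11.5 for the order of sources. The ratios of 0.75 to 0.97 rest on the assumed rise to the maximum and show direction and possible size only.

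**What to change.** Amend SAP 2.4.1, 2.7 and 3.7 before database lock:

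1. Use device data from Visits 3 and 4 as the main source for each item the device stores. For Vital Compact these are sessions, duration, and average and maximum intensity.
2. Use the diary where memory was erased or overwritten, or where the device does not log the item (possibly itouch average intensity). Report how many women this applies to, by arm.
3. Define average intensity. Label diary intensity as maximum (self-reported), and do not place it in the 2.7 bands without saying so.
4. State the source for the per-protocol compliance criterion.
5. Keep a diary-based summary in both arms as the like-for-like comparison.
6. List any remaining departure from the protocol in section 4.

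One detail needs a rule. The Vital Compact counter includes partial sessions, so a woman who always splits into three would show 180/60 = 300% of target use. Total minutes divided by 30 avoids this.

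The cost is SAP wording and some programming, since both records are already planned. The drawback is that the two devices may log different items, so some summaries will rest on different sources by arm; the parallel diary summary makes that visible.
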